## **Background**

### *Psychosis*

Psychosis is a severe mental disorder with the main and common symptom being loss of reality testing due to misinterpretation of perception. The disorder is often accompanied by more or less life-long social impairment and decreased level of functioning. No biological correlates are available so the diagnosis is based on the presence of symptoms. The most serious form of psychosis, schizophrenia, has a lifetime prevalence of 5.5(SD 4.5) in 1000 persons and the incidence is 23.7(SD 30.3) in 100 000 persons. Mean age of onset is 18 years in men and 25 in women. Schizophrenia is associated with elevated suicide rates and an increased risk of premature death related to a wide range of somatic conditions, mainly depending on increased metabolic risk factors. The median standardized mortality ratio is 2.6 for all-cause mortality and this differential gap has increased over the recent decades. Several modifiable unhealthy life style factors are more prominent in individuals with schizophrenia, such as smoking, unhealthy dietary habits and decreased physical activity. Tobacco use and weight gain/obesity has also been shown to be associated with increased severity of symptoms and decreased level of functioning.

Cognitive impairment represents a core feature in schizophrenia with individuals experiencing various degrees of decline from expected level of cognitive functioning. The majority (70 %) function at a level at least one standard deviation below that of healthy controls, with impairment already present in first-episode psychosis, and enduring after pharmacological treatment. Impairments are found in the domains of attention, verbal learning, memory, working memory, processing speed, problem solving/executive functioning and social cognition, in addition to a global cognitive deficit. The presence of cognitive impairments is further associated with a more severe course of illness and a higher rate of use of health services. Cognitive impairment is a prominent predictor of functional outcome in psychotic disorders and may strongly affect the level of independence the affected persons can achieve in their lives. Intact cognition is essential for occupational performance and academic functioning, hence cognitive deficits are frequently associated with unemployment and curtailed level of education.

Depression is a common comorbidity in schizophrenia with reported rates of 25-81%. Persons affected by comorbidity have lower levels of medication adherence, more substance related problems, poorer social and family relationships and poorer quality of life.

Another problem in schizophrenia is the tendency of relapses. Many individuals with schizophrenia have several relapses resulting in multiple hospital stays, making it a leading cause of disability worldwide.

The stress-diathesis model suggests that lowering biological vulnerability or reducing stress can prevent relapses. Most of the used strategies, such as antipsychotic medication and avoiding substance abuse, focus on biological vulnerability. During the past three decades' psychosocial interventions have emerged focusing on increasing resilience to stress and building social support. These strategies often involve support for life style changes targeting smoking cessation, dietary habits and physical exercise. Advice on physical exercise are however often general and only very rarely organized exercise sessions are offered.

In summary there are three areas of suboptimal management of people with schizophrenia; 1) lack of effective treatments for negative symptoms and cognitive dysfunction, 2) only partially effective treatment for positive symptoms 3) high rates of physical health problems, particularly cardiovascular disease.

### *Recovery*

The non-linear process of recovery needs to be consumer led. This means that the traditional medical and psychosocial rehabilitation model needs to be abandoned. The care system needs to provide the tools and support when needed but the responsibility should lie on the affected person. In other care disciplines the patients' autonomy is well respected but psychiatry lags behind.

### *Stigma*

All persons develop conception of mental illness early in life and form expectations of rejection. If affected this fear of rejection will have serious negative consequences. Such consequences are decreased self-esteem, self-efficacy and recovery orientation. Another consequence is social phobia, which is a very common comorbid disorder in schizophrenia. Stigma is an important factor in the decreased social capability, hindering studies and employment.

### *Physical exercise*

Aside from the effects on the cardiovascular and muscular system, physical activity also has several neurobiological effects. It is reported to modulate the Hypothalamic-pituitary-renal (HPA) axis, which is a part of the stress-response system. It also affects the serotonergic drive thus acting like an antidepressant. The neural growth factor expression is increased by physical exercise affecting the neurogenesis in the brain. This effect can be seen in studies showing enhanced cognition (learning and memory) in healthy persons. There are numerous psychological effects such as increased wellbeing and heightened motivation and diversion from negative thoughts. However, physical activity is a complex behavior, including exercise (high-intensity, short-term bouts of physical activity, often structured), everyday physical activity (including those from daily chores, traveling, work and leisure time), as well as sedentary behaviors. In addition, physical fitness (primarily aerobic fitness) is a consequence of those behaviors and may well have its own independent relation and effect on cognition, sleep and mood.

### *Physical exercise as a treatment in psychosis*

A recently reported pilot study in young persons at high risk for psychosis showed improvement in positive and negative symptoms, social and role functioning, performance on neurocognitive tests and cardiovascular fitness.

Thus far, only few studies have examined physical exercise in psychosis and differences in methodology makes them difficult to compare. A Cochrane Review from 2010 concluded that regular exercise programs are possible and may potentially have beneficial effects on both physical and mental health as well as overall wellbeing. However, only 3 studies fulfilled the inclusion criteria with small sample sizes and the exercise conditions and outcome measures differed. A systematic review and meta-analysis from 2014 including 8 studies showed only a modest increase in levels of exercise activity and no changes in symptoms or Body Mass Index (BMI). However, the included studies varied in exercise programs, age groups, sample size and outcome measures.

Cognitive functioning after exercise has only rarely been the focus with only one small study reporting a 34% improvement in short-term memory.

The treatment potential is large since individuals affected with serious mental illness are more likely to be sedentary than the general population.

### **Preliminary results Fitforlife pilot study**

During 2015-2016, 99 participants were included. A majority were males (60 persons) and the mean age was 28.2 years. The study was originally designed as a waiting list study but due to

problems with the open care units this turned out to be impossible. Of the 99 persons 39 did not attend any sessions, the rest attended between 1-52 sessions, mean 13.1(SD 12.1). Trailmaking A test time (visual attention) improved 8.5 seconds (SD 20.4) in those that attended >1 session and 5.4 (SD 6.5) in those that did not attend. Trailmaking B, (visual attention and task shifting), improved 10.4 seconds (SD 42.8) in attenders versus 4.6 (SD 31.7) in non-attenders.

Camberwell assessment of need showed that at the initial examination 33 persons reported difficulties with social contacts while at the end of the intervention 17 of those reported no problems. Likewise, 24 persons reported problems with close relations at baseline while 11 of them reported no problem at the end. In the proposed study this will be measured in a more extensive way. During an open house for participants and relatives there were reports about improvement in daily life such as "started to care about his looks", "cleans his room". During spring 2017 the cognitive tests will be analysed and linked with inflammatory markers. The study has given us experience on how to organise exercise for persons with psychosis. After the first wave four participants were educated as peer mentors. At least one peer-mentor was present in all sessions in wave two and three. The peer mentors were responsible for organizing parts of the sessions under supervision of educated trainers. Since the study finished the mentors have worked as peer mentor trainers, offering sessions to patients at an open care unit for FEP. The staff promote the sessions during their meetings with their patients and discussion about physical activity levels is a part of all patients' individual care programme.

**Study objectives:** See separate information

## **Methodology**

Study design: Non randomized open trial.

*Study population:* Patients affected by psychosis at open care psychiatric units who are responsible for taking care of psychosis in Sweden.

*Sample size:* Our aim is to recruit 300 patients including mentors at each unit.

*Variables list including data collection tools:*

1. From the medical records: age, gender, diagnosis, time of first contact with psychiatry, medication
  - App questions on overall function using WHODAS 2.0
  - App question on social network: qualitative and quantitative
  - App questions: smoking, alcohol consumption and illicit drug use
  - Cognitive tests: Cogstate (performed at a computer) and Trail making A and B
  - Submaximal fitness test: Åstrand
  - Physical activity pattern, including sedentary time, low-intensity physical activity and exercise, assessed by a simple accelerometer on a subsample.
  - Body measurements: length, weight, hip-waist measure, blood pressure.
  - Blood samples: Blood lipids, HBA1C, TNFalfa, CRP, Il-6

*Plan of analyses:* See separate information

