## **Intervention including time plan**

A team consisting of one of the mentors from Fitforlife, a health pedagogic, and one or two from the research group will come to each included open care unit.

Day 1; Upstart meeting led by a research group member.

Day 1-4; Education of the new mentors led by the health pedagogic assisted by mentor(s) from Fitforlife pilot study.

Day 1-5; Baseline examinations (see above for data collection tools) of all the potential participants by the local contact person(s).

Day 5-14; Start of the training. Initially supported by the health pedagogic and the mentor(s) from Fitforlife pilot study.

Day 14-70: Training sessions led by the local mentors. Supported by phone and online by the health pedagogics and the mentors from Fitforlife. During this time 1-3 visit(s) from the health pedagogic to each mentor during a training session.

Day 70-75: Follow up assessments by the local contact person.

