#### **Strengths and limitations**

Largest study of physical exercise in psychosis. Using an entirely new concept, patients lead physical exercise.

Not randomized due to practical issues. Impossible to randomize patients within a unit, many ongoing group activities. Differences between units in care programme large making cluster randomization difficult.

**Ethical permission:** See separate information

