### **Statistical analysis plan**

Baseline descriptions will be presented and used in the different analyses to see if gender, duration of psychosis, neuroleptics affects the different outcomes.

The main outcome social function will be analyzed using  $\chi^2$  tests and analysis of variance for categorical outcomes using data from baseline to 6 months. Pre- to post-intervention (within-group) analyses will be performed using paired-sample *t*tests, with effect sizes (Hedges' *g*) calculated for statistically significant values. The participants will be divided according to attended number of training sessions. This will be done in quartiles and used to look at between group differences (analysis of covariance- ANCOVA). A sub analysis will be done including those with accelerometer data from the entire study period. Baseline score will be included as covariates in each model.

Parametric test assumptions will be checked before running all analyses. Normality will be assessed using the Shapiro–Wilks test and normal probability plot, and homogeneity of variance using Levene's test. For analyses involving unequal sample sizes, Welch's test might be considered. Similar procedures will be used when analyzing blood samples, inflammatory and metabolic markers as well as cognitive test data. Normative data from the cog state data base will be used for comparison. Multilevel analysis will be used taking into account the included open care units.

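### Peer mentors count towards the 300 and the SAP does not separate them, so by default the mentor role is mixed into the attendance-quartile comparison

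*Protocol*

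**What the plan says.** The protocol (Methodology, sample size) states: "Our aim is to recruit 300 patients including mentors at each unit". I read this as 300 in total, with the mentors at the various units among them. Mentors are themselves patients; Strengths and limitations describes the approach as "Using an entirely new concept, patients lead physical exercise".

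The time plan gives mentors elements that other participants do not have:

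- Education at the start: "Day 1-4; Education of the new mentors led by the health pedagogic". The baseline examinations of all potential participants are scheduled for Day 1-5, so the two windows overlap.
- Delivery of the programme: "Day 14-70: Training sessions led by the local mentors". The phone and online support named next is most naturally read as support for these mentors.
- Supervision: "During this time 1-3 visit(s) from the health pedagogic to each mentor during a training session".

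The SAP names social function as the main outcome. It plans paired t-tests for within-group change and then an attendance analysis: "The participants will be divided according to attended number of training sessions". The division is into quartiles, compared by ANCOVA. The factors it names are baseline score, gender, duration of psychosis, neuroleptics and open care unit. Mentor status does not appear as a covariate, stratum, exclusion or sensitivity analysis.

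**The concern.** The study has no randomised control group, so the attendance quartiles are the only between-group comparison the SAP defines by exposure to the programme. A reader will take a gradient across quartiles as evidence that more exercise brings more improvement.

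Mentor status can produce such a gradient by itself. It probably raises attendance, because the sessions need someone to lead them. It may also alter social function directly, because being trained and given responsibility for a group is a social intervention in its own right. A factor that plausibly drives both exposure and outcome is a confounder of the attendance comparison.

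The planned adjustments do not reach it. The baseline score is meant to be measured before the role takes effect, so it cannot capture what the role does afterwards. The unit level in the multilevel model separates units, whereas mentors and non-mentors sit side by side within each unit.

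**Working it through.** **The plan's own figure.** The 300 is a recruitment aim. No alpha, power, effect size, SD or dropout rate is given, so there is no calculation to reproduce.

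**Inputs from the documents.** N = 300, mentors included; attendance split into quartiles, hence 300/4 = 75 per group.

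**Inputs assumed, because the documents give none.** Mentor share m = 5%, 10% or 20% (M = 15, 30 or 60). Extra standardised change in mentors d = 0.2 to 0.5 SD. All mentors in the top quartile. Complete data, SD of 1 and two-sided alpha 0.05.

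**Formulas.**

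- Mentor share of the top quartile = M/75.
- Shift in the top-minus-bottom contrast (Q4-Q1) = (M/75) × d.
- Shift in the overall pre-post mean = (M/300) × d, one quarter of the Q4-Q1 shift.
- Probability of a significant Q4-Q1 result when non-mentors show no difference: normal approximation with standard error sqrt(2/75) = 0.163.

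| Mentors | Share of top quartile | Q4-Q1 shift (SD) | Pre-post shift (SD) | P(significant Q4-Q1) |
|---|---|---|---|---|
| 15 | 20% | 0.04 to 0.10 | 0.010 to 0.025 | 6 to 9% |
| 30 | 40% | 0.08 to 0.20 | 0.02 to 0.05 | 8 to 23% |
| 60 | 80% | 0.16 to 0.40 | 0.04 to 0.10 | 17 to 69% |

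Worked example: 30 mentors and d = 0.5 give (30/75) × 0.5 = 0.20 SD. Then 0.20/0.163 = 1.22 standard errors, and the rejection probability is 23% instead of 5%.

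**If mentors share sessions.** Suppose half the mentors fall in the top quartile and the rest spread evenly over the other three. The bottom quartile then holds one sixth of them, and the shift becomes (M/75) × (1/2 - 1/6) × d, one third of the tabulated value: about 0.01 to 0.13 SD. If mentors spread evenly over all four quartiles, the shift is zero.

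**Cost of analysing non-mentors only.** Interval widening = sqrt(300/(300 - M)):

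- M = 15: sqrt(300/285) = 1.026
- M = 30: sqrt(300/270) = 1.054
- M = 60: sqrt(300/240) = 1.118
- M = 80: sqrt(300/220) = 1.168

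The Q4-Q1 difference detectable with 80% power is (1.960 + 0.842) × sqrt(2/n per quartile). It moves from 0.457 SD at N = 300 to 0.469, 0.482 and 0.511 SD for 15, 30 and 60 mentors.

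**Limit of the illustration.** In the pilot, 39 of 99 attended no session. At that rate about 300 × 39/99 = 118 of 300 would have zero sessions, more than one quartile, so four equal groups of 75 are themselves an approximation.

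**The case against.** The SAP never says that mentors are analysed as ordinary participants. The sample-size sentence is a recruitment aim, and their inclusion is inferred from silence. That is correct. Even so, nothing in either document points the other way, and an analyst following the SAP would include them.

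A reader might infer that mentors fill the top quartile by design. The documents do not support this. Sessions are led by the local mentors as a group, and no mentor is required at every session. The pilot trained four mentors and reports at least one at each session in waves two and three, which fits a rota. Concentration in the top quartile is likely, but its degree is unknown.

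Selection of better-functioning patients as mentors is partly handled: paired tests remove stable differences in level, and ANCOVA adjusts for baseline score. What remains is differential change. The supervision visits also take place during sessions at which other participants are present, so that element is not wholly exclusive to mentors.

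A reader might also infer that the overall pre-post result is invalid because it mixes two roles. It is not. Patient leadership is part of the programme, and the change in all patients is a legitimate whole-programme estimate. The possible shift there is also the smaller one.

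Finally, attendance is self-selected even among non-mentors, so removing mentors does not make the comparison causal. That stands. It does remove one identifiable and avoidable source of confounding.

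**Conclusion.** The point holds for the attendance analysis. Mentors are counted in the sample, have a distinct role, and are not separated in the SAP, so the planned quartile comparison mixes mentor role with attendance. The effect on the Q4-Q1 contrast could be negligible or could reach 0.40 SD within the assumed range. The upper end needs 60 mentors, all in the top quartile, and an extra change of 0.5 SD; none of these comes from the documents. The direction is also open: if the role were a burden, the shift would reverse.

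For the pre-post change the point is one of description and sensitivity. The overlap between the baseline window and mentor education is a possible contamination only. Nothing says that mentors are examined after education begins, and the documents show no effect of those days on baseline scores.

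**What to change.** 1. Record mentor status as a flag, and report the number of mentors per unit and their attendance.
2. Cut the attendance quartiles among non-mentors and run the ANCOVA in non-mentors only. Give the all-participant version as a sensitivity analysis.
3. Keep the all-patient pre-post result as the whole-programme estimate. Add a non-mentor sensitivity analysis and describe the mentors separately.
4. Where feasible within the Day 1-5 window, take mentors' baseline measurements before their education. Otherwise, record the order.

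The cost is SAP wording, one variable and some scheduling effort, since both windows open on Day 1. Attendance-analysis intervals widen by about 3 to 12% for 15 to 60 mentors, and by about 17% at 80. The all-patient pre-post estimate loses no precision.

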#### *Measurements during the intervention*

Compliance will be measured by the local coordinators. In a subgroup objective measures of physical activity using simple accelerometers will be performed.

Before and after each training session the participant will be asked to answer simple App based questions - "How do you feel" (happy, tired etc).

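### The attendance-quartile ANCOVA on social function may be confounded by comorbid depression, which the plan neither clearly records at baseline nor names as a covariate

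*Protocol*

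**What the plan says.** The trial is non-randomised (Protocol, Methodology). The SAP divides participants by number of sessions attended and states: "This will be done in quartiles and used to look at between group differences (analysis of covariance- ANCOVA"). The baseline score enters each model. The SAP also looks at gender, duration of psychosis and neuroleptics, and it plans a multilevel analysis for the care units. Depression, social phobia and mood do not appear.

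The Methodology variables list takes "From the medical records: age, gender, diagnosis, time of first contact with psychiatry, medication". It adds "App questions on overall function using WHODAS 2.0", social network questions and "App questions: smoking, alcohol consumption and illicit drug use". It contains no depression, anxiety or psychotic-symptom measure.

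The only mood item is tied to sessions: "Before and after each training session the participant will be asked to answer simple App based questions" (Protocol, Measurements during the intervention).

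On the conditions themselves, the Psychosis section of the background says "Depression is a common comorbidity in schizophrenia with reported rates of 25-81" per cent, and then: "Persons affected by comorbidity have lower levels of medication adherence, more substance related problems, poorer social and family relationships and poorer quality of life". The Stigma section says: "Another consequence is social phobia, which is a very common comorbid disorder in schizophrenia".

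**The concern.** Attendance is chosen by the participant, so the quartiles differ in whatever drives attendance. The protocol itself describes depression as going with poorer adherence and poorer social relationships, which makes it a natural candidate for a common cause of low attendance and poor social function. Social phobia is a plausible second candidate in a programme of organised training sessions.

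The baseline score removes only the part of such a difference that already shows at baseline. If depressed participants attend less and also do worse at follow-up from the same baseline score, the high-attendance quartiles look better even when exercise does nothing. With no clearly specified baseline record of depression and no planned adjustment, the reported analysis could not show whether this had happened.

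The session mood answers do not fill the gap. They start after baseline, and people who never attend have none. In the pilot 39 of 99 participants (39%) attended no session. If that recurred among 300, about 0.39 × 300 ≈ 118 people would have no mood value, which is more than a whole quartile of 75.

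**Working it through.** **No plan figure to reproduce.** The target of 300 is given without alpha, power, effect size or SD. The check therefore compares the texts and then illustrates the possible size.

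**Texts side by side**

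| | Depression | Social phobia |
|---|---|---|
| Link to taking part | Stated for medication adherence, not for exercise sessions | None stated; inference |
| Link to social function | Stated (social and family relationships) | Indirect: reduced social capability is attributed to stigma |
| Recorded at baseline | Only if the undefined diagnosis and medication fields include it | Only if the undefined diagnosis field includes it |
| Covariate in the SAP | No | No |

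**Inputs for the illustration.** From the documents: n = 300, four quartiles of 75, depression in 25–81%. Assumed:
- no exercise effect;
- baseline/follow-up correlation 0.7;
- depressed participants 0.5 SD lower at baseline;
- attendance propensity lower by d = 0.5 or 0.8 SD in the depressed;
- follow-up worse by g = 0, 0.2 or 0.4 SD in the depressed at the same baseline score.

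The score is coded so that higher is better.

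**Step 1, approximate bias.** Bias (top minus bottom) ≈ g × Δp, where Δp is the share depressed in the bottom quartile minus that in the top. With prevalence p, attendance follows a mixture of two normals. The lower cut-point q₁ solves p·Φ(q₁ + d) + (1 − p)·Φ(q₁) = 0.25, and the share depressed in the bottom quartile is p·Φ(q₁ + d)/0.25. The top quartile is handled the same way. At p = 0.5:
- d = 0.5: 65.6% against 34.4%, Δp = 0.31; with g = 0.4 the bias is 0.4 × 0.31 = 0.12 SD.
- d = 0.8: 74.1% against 25.9%, Δp = 0.48; with g = 0.4 the bias is 0.4 × 0.48 = 0.19 SD.
- g = 0.2, d = 0.5: 0.2 × 0.31 = 0.06 SD.
- g = 0: bias 0, whatever Δp is.

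**Step 2, against the precision.** The residual SD after baseline adjustment is √(1 − 0.7²) = 0.714. The standard error of a two-quartile difference is 0.714 × √(2/75) = 0.117 SD. A bias of 0.19 SD is thus about 1.6 standard errors, and 0.06 SD about half of one.

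**Step 3, simulation** of the quartile ANCOVA with baseline score (3-df test at 5%, 1,500 to 3,000 runs per scenario, 50% depressed). Ranges are across repeat simulations.

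| g | d | Bias (SD) | Rejection | Rejection with a perfect depression indicator added |
|---|---|---|---|---|
| 0 | 0.5 | about 0 | about 5% | about 5% |
| 0.2 | 0.5 | 0.06 | 6–7% | about 5% |
| 0.4 | 0.5 | 0.12 | 11–12% | 5–6% |
| 0.4 | 0.8 | 0.18–0.19 | 23–24% | about 5% |
| −0.2 (depressed improve more) | 0.5 | −0.06 | about 7% | about 5% |

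At 25% and 81% prevalence, with g of 0.2 to 0.4, the bias is about 0.03 to 0.14 SD.

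**Step 4, imperfect records.** Suppose records capture half the cases with no false positives (assumed), and depression is present in 50% of low and 30% of high attenders, a crude difference of 0.20. Among those with no recorded diagnosis, the shares truly depressed are 0.25/0.75 = 0.333 and 0.15/0.85 = 0.176, a difference of 0.157. Among those with a recorded diagnosis the difference is 0. Least squares weights each stratum by its size times the variance of group membership: 0.8 × 0.249 = 0.199 without a record and 0.2 × 0.234 = 0.047 with one. The remaining difference is 0.157 × 0.199/(0.199 + 0.047) = 0.127, about 63% of 0.20. In the strongest simulated case, 50% sensitivity leaves 0.13 of 0.18 SD (about 72%), with rejection about 13%. At 70% sensitivity it leaves 0.09 SD and about 8%.

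**The case against.** A reader might infer that depression and social phobia are not recorded at all, that the comparison is therefore confounded, and that no later model could correct it. The documents do not support that reading.
- The diagnosis and medication fields are not limited to psychosis, so comorbid diagnoses and antidepressants may already be meant. The text is ambiguous, not silent.
- Participants are followed through medical records for 12 months (Protocol, Long term follow-up), so diagnoses already on file could be extracted later. Only baseline mood and unrecorded cases are lost.
- The adherence that the protocol mentions is to medication. For social phobia no attendance link is stated, and the functional link runs through stigma.
- The background describes poorer social relationships, which is a level, and the baseline score is in every model. Bias needs a different course from the same baseline, which no passage states. Without that the bias is about 0, and with the opposite course its sign reverses.

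All four points stand. It is also fair to say that the attendance ANCOVA is only part of the analysis, that motivation or negative symptoms could equally drive attendance, and that one momentary mood question is no depression scale.

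These points do not remove the gap. An undefined field does not ensure that local staff extract comorbidities, and a confounder supported by the protocol's own background is still missing from the planned model.

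**Conclusion.** The concern holds in a limited form. The attendance comparison may be confounded by comorbid depression and plausibly by social phobia. Baseline recording of both is left unclear, and neither is a planned covariate. In the scenarios run, the bias lies between about 0 and 0.19 SD, with rejection between about 5% and 24% when exercise has no effect; the upper end needs a 0.4 SD residual effect and a 0.8 SD attendance gap. Size and direction both rest on assumed inputs. This is a worthwhile, low-cost improvement to one analysis. It does not show that the attendance result will be wrong, and it does not bear on the paired pre-post tests.

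**What to change.** **Protocol, Methodology (variables list).** State that comorbid depressive disorder, social phobia and antidepressant treatment at baseline are extracted as separate fields from the same medical records. Ask the existing App mood question once of every participant during the Day 1–5 baseline examinations, whether or not they go on to attend. Asking it again at Day 70–75 is not needed for this adjustment.

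**SAP.** Add these baseline values to the attendance ANCOVA, report the results with and without them, and describe the comparison as associational. That description also covers confounders that nobody measures.

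**Cost.** Three fields from records already in use, one existing question at an existing assessment, and a few degrees of freedom out of 300 participants. The limit should be stated openly: records are incomplete and a single mood item is crude, so with 50% record sensitivity roughly 60–75% of any bias may remain.
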